Elevated liver parameters during double-blind treatment will be summarized: the number (%) of subjects meeting the criteria defined below within a given central laboratory sample will be tabulated by dose group. Percentages will be based on the number of subjects at risk: those not meeting the criterion at baseline (or having a missing baseline value) and having at least one post-baseline value for a given parameter and treatment period.

- Aspartate aminotransferase (AST) or alanine aminotransferase (ALT) > 3 × upper limit of normal (ULN)
- AST or ALT > 5 × ULN
- AST or ALT > 10 × ULN
- TBIL > 1.5 × ULN and 2 × ULN
- Alkaline phosphatase > 1.5 × ULN
- (ALT or AST > 3 × ULN) and (TBIL > 2 × ULN)

All AST and ALT values for subjects with an AST or ALT > 3 × ULN will be listed.

### 10.3 Vital signs, weight and physical examination

Each summary and listing will include unscheduled assessments. Assessments from supine and sitting position will be presented together.

Absolute changes from baseline (mean of the first and second morning values after the PSG nights at V2, run-in period) to Days 1 and 2 (mean of the first and second morning values after the PSG treatment nights of each treatment period) in vital signs (systolic and diastolic blood pressure, pulse rate and body temperature) will be summarized. The absolute values at baseline and Days 1 and 2 will also be summarized.

The changes from baseline (V1 or last value before double-blind treatment) to V7 (or last value on or following double-blind study treatment) in body weight will be summarized as one group (i.e., All subjects).

Physical examination abnormalities will be listed.

### 10.4 Electrocardiograms

Unless noted otherwise, ECG summaries and listings will include unscheduled assessments.

The absolute change from baseline (V2, second morning) to the second morning of the PSG nights of each treatment period for ECG parameters (QTcF, QTcB, heart rate, PR, QRS) will be summarized. The absolute values will also be summarized. Only scheduled assessments will be considered for these summaries.

Marked ECG abnormalities are defined in Table 4 below. A marked ECG abnormality will be assigned to the dose group where it is present regardless of its presence in previous treatment periods.

The number (%) of subjects meeting the criteria of a marked ECG abnormality will be tabulated. Percentages will be based on the number of subjects at risk: those not meeting the criterion at baseline (or having a missing baseline value) and having at least one post-baseline value for a given parameter and treatment period.

All ECG values for subjects with at least one marked ECG abnormality will be listed.

**Table 4** Marked abnormalities in ECG parameters

ECG parameter	Criteria for marked ECG abnormalities
QTcF, QTcB (ms)	> 450 and ≤ 480 (H) > 480 and ≤ 500 (HH) > 500 (HHH) > 30 and ≤ 60 increase from baseline (HH) > 60 increase from baseline (HHH)
HR (bpm)	< 45 (LLL) < 50 (LL) > 10 and ≤ 20 decrease from baseline (LL) > 20 decrease from baseline (LLL)
PR (ms)	> 200 (HH)
QRS (ms)	> 110 (HH)

HR = heart rate; QTcB = QT interval corrected according to Bazett's formula; QTcF = QT interval corrected according to Fridericia's formula. LL, LLL, H, HH, HHH = flags for low and high marked abnormalities.

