6.2 Safety endpoints

- TEAEs⁷ up to 5 days after study treatment discontinuation
- SAEs up to 30 days after study treatment discontinuation
- AEs leading to premature discontinuation of the double-blind study treatment
- AEs of special interest starting or worsening after the first dose of the first treatment period until EOS (and after adjudication by the ISB):
 - Narcolepsy-like events (e.g., excessive daytime sleepiness, cataplexy)
 - Complex sleep behavior events.
 - Suicidal thoughts and/or behaviors.
- Change from Baseline (mean of the two PSG nights at V2, run-in period) to the Days 1 and 2⁸ of each period in vital signs (systolic and diastolic BP, pulse rate and body temperature)
- Change from Baseline (V1) to the second morning after the PSG nights at V7 in body weight
- Treatment-emergent ECG abnormalities from V3 until EOT
- Change from Baseline (V2, second morning) to the second morning after the PSG nights at V3, V4, V5, V6 and V7 in ECG parameters
- Marked laboratory abnormalities on double-blind study treatment
- Change from Baseline (V2, second morning) to the second morning after the PSG nights at V3, V4, V5, V6 and V7 in laboratory variables
- Change from Baseline (mean of the two PSG nights at V2, run-in period) to Days 1 and 2⁸ of each treatment period in:
 - Digit Symbol Substitution Test (DSST[®]) performed in the morning, 30–60 minutes after lights on
 - Sheehan Disability Scale (SDS[®]) performed in the morning, 30–60 minutes after lights on
 - Karolinska Sleepiness Scale (KSS) performed in the morning, 30–60 minutes after lights on
- Incidence of most severe suicidal ideation and suicidal behaviors according to the C-SSRS[®] for each treatment period.

⁷ A TEAE is any AE temporally associated with the use of study treatment from Day 1 until 5 days after last study drug intake in each treatment period and until 5 days after study treatment discontinuation whether or not considered by the investigator as related to study treatment.

⁸ Days 1 and 2 is the mean of the first and second morning values after the two PSG nights of a treatment period.

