7.2.4.9 ECG assessment

A standard 12-lead ECG is to be performed, at V1 and in the second morning of V2, V3, V4, V5, V6 and V7.

12-lead ECG will be recorded at rest with the subject in the supine position for a 5-minute period. Data records will be sent to the evaluation center for central reading.

Details will be provided in the 12-lead ECG laboratory manual.

The following parameters will be evaluated: PQ or PR (ms), QRS (ms), QT (ms), heart rate [HR] (bpm), and rhythm. QT_C (ms) will be calculated according to

- Bazett's formula: $QT_C = QT / (RR)^{1/2}$
and
- Fridericia's formula: $QT_C = QT / (RR)^{1/3}$, where $RR = 60 / HR$

If the central review of the ECG detects a prolonged QTc interval greater than 450 ms for a subject at screening (V1, V2), ECG must be repeated (at least 30 minutes after first ECG on the same day). If the central review confirms that the repeated ECG shows a QTc interval greater than 450 ms, the subject cannot be enrolled into the study.

Clinically relevant findings made after randomization that meet the definition of an AE must be recorded in the eCRF.

ECG data collected by the CRO will be electronically transferred to Actelion.

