10.3.5.4 ECG

Incidence of clinically abnormal ECG on double-blind study treatment as well as treatment-emergent ECG abnormalities will be tabulated (frequency and percentage) by dose.

On-treatment change in ECG parameters will be described using descriptive statistics.

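### SAP 10.4 counts only numeric ECG limits: the protocol's by-dose tables of clinically abnormal ECGs and of new rhythm or other qualitative findings are missing, and the omission is not declared

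*SAP*

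**What the plan says.** **Protocol.** Section 6.2 lists among the safety endpoints "Treatment-emergent ECG abnormalities from V3 until EOT", and 10.2.4.3 repeats it. Section 7.2.4.9 sends the recordings for central reading and specifies: "The following parameters will be evaluated: PQ or PR (ms), QRS (ms), QT (ms), heart rate [HR] (bpm), and rhythm". Section 10.3.5.4 sets the reporting: "Incidence of clinically abnormal ECG on double-blind study treatment as well as treatment-emergent ECG abnormalities will be tabulated (frequency and percentage) by dose". Section 10 leaves full details of the analyses to the SAP.

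**SAP.** Section 10.4 plans two kinds of ECG table. One is descriptive: absolute values and change from baseline "for ECG parameters (QTcF, QTcB, heart rate, PR, QRS) will be summarized". The other is categorical: "The number (%) of subjects meeting the criteria of a marked ECG abnormality will be tabulated". Table 4 defines those criteria as QTcF or QTcB level and increase from baseline, PR above 200 ms, QRS above 110 ms, and for heart rate "< 45 (LLL) < 50 (LL) > 10 and ≤ 20 decrease from baseline (LL) > 20 decrease from baseline (LLL". The denominator is restricted to subjects at risk, described as "those not meeting the criterion at baseline (or having a missing baseline value", who also have a post-baseline value in the period.

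SAP 12.1 declares one change from the protocol, which concerns the analysis set for secondary and exploratory efficacy endpoints. Sections 12.2 and 12.3 are marked not applicable.

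**The concern.** The protocol names two things to be counted by dose. One of them, the clinically abnormal ECG, is a judgement on the tracing, which interval limits cannot stand in for. The other is wider than interval limits, because rhythm is evaluated alongside the measurements. The SAP carries forward only what can be expressed as a number crossing a limit.

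What is at stake is part of a stated safety endpoint, in subjects aged 65 or over. A clinical study report that follows the SAP as written could not say how many subjects on each dose had a clinically abnormal ECG or a new rhythm finding. Because section 12 is silent, a reader of the SAP would not know that the protocol had promised those counts.

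**Working it through.** The plan states no figure to reproduce here. The check has two parts.

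**1. Protocol item against SAP output**

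| Protocol item | Where promised | SAP output |
|---|---|---|
| Clinically abnormal ECG, n (%) by dose | 10.3.5.4 | None |
| Treatment-emergent abnormality, numeric | 6.2, 10.2.4.3, 10.3.5.4 | Table 4 counts; the at-risk denominator makes them in effect treatment-emergent |
| Treatment-emergent abnormality, rhythm or other qualitative | 6.2 and 10.3.5.4, with rhythm evaluated under 7.2.4.9 | None |
| Change in ECG parameters | 6.2, 10.2.4.3 | Descriptive summaries in 10.4 |
| Declaration of any dropped analysis | SAP section 12 | None for ECG |

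**2. Which arrhythmias would Table 4 miss?**

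The formulas are those of Protocol 7.2.4.9: QTcB = QT / RR^(1/2) and QTcF = QT / RR^(1/3), with RR = 60 / HR. All ECG values below are assumptions chosen for illustration, not trial data. The assumed baseline is HR 65, QT 390 ms, PR 160 ms and QRS 90 ms. RR is then 60/65 = 0.923, so QTcB = 405.9 and QTcF = 400.5.

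| Illustrative on-treatment ECG | HR | QT | QTcB (change) | QTcF (change) | Table 4 flag |
|---|---|---|---|---|---|
| New atrial fibrillation, PR not measurable, QRS 90 | 70 | 380 | 410.4 (+4.5) | 400.0 (-0.5) | None |
| Ectopy, PR 160, QRS 90 | 66 | 388 | 406.9 (+1.0) | 400.5 (0.0) | None |
| Supraventricular tachycardia, PR 150, QRS 90 | 130 | 290 | 426.9 (+21.0) | 375.3 (-25.2) | None |
| Tachycardia, PR 150, QRS 90 | 130 | 320 | 471.0 (+65.1) | 414.1 (+13.6) | QTcB level and increase |
| Junctional bradycardia, PR not measurable, QRS 95 | 44 | 440 | 376.8 (-29.1) | 396.8 (-3.7) | Low HR and HR decrease (21) |

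The third and fourth rows share a rate but not a result, so the boundary is worth working out. From this baseline, Table 4 flags a QTcB above 405.9 + 30 = 435.9 ms.

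- At 130 bpm, RR^(1/2) = (60/130)^(1/2) = 0.679, so a QT above about 435.9 x 0.679 = 296 ms is flagged.
- At 115 bpm, RR^(1/2) = (60/115)^(1/2) = 0.722, so a QT above about 435.9 x 0.722 = 315 ms is flagged.

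The set that escapes is therefore specific: heart rate at least 50 bpm and no more than 10 bpm below baseline; QTcF and QTcB each at most 450 ms and up by no more than 30 ms; PR at most 200 ms or not measurable; QRS at most 110 ms.

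**The case against.** The strongest reply is that the protocol never defines a treatment-emergent ECG abnormality and leaves the detail to the SAP, and that the SAP supplied a definition. Table 4 excludes subjects who already meet the criterion at baseline, and SAP section 4 presents summaries by dose group. That is a treatment-emergent table by dose. This stands for the numeric limits. A reader might infer that the SAP drops the treatment-emergent endpoint altogether, and the documents do not support that. The reply does not reach the clinically abnormal count, which the protocol names separately, or rhythm.

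A second reply is that nothing vanishes. SAP section 10 has all safety data listed. Protocol 7.2.4.9 requires clinically relevant findings that meet the adverse-event definition to be recorded, the definition in 9.1.1 covers new or worsened clinically significant ECG findings, and SAP 10.1 tabulates adverse events. This also stands, and a sustained new arrhythmia would be a likely candidate for that route. But a listing is not a frequency by dose, and the protocol keeps ECG abnormalities as an endpoint apart from adverse events.

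A third reply concerns heart rate. The Table 4 limits are all on the low side, and a reader might infer that every high or rising rate is lost from the ECG tables. It is not: 10.4 summarises heart rate and its change, and section 4 includes the minimum and maximum in continuous summaries. What is absent is a count of subjects above a limit. No protocol text on ECG analysis asks for one, so the one-sided limits are not a conflict between protocol and SAP.

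Finally, the ECG laboratory manual is not part of these documents. They show that rhythm is evaluated. They do not show that coded morphology or conduction terms, or a central normal/abnormal call, are collected.

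**Conclusion.** The point holds as a reporting gap. One tabulation that the protocol promises (clinically abnormal ECGs by dose) is absent from the SAP, the qualitative part of a second (treatment-emergent abnormalities) is absent too, and neither omission is declared. The text comparison alone establishes this; the illustrative ECGs only show which findings would go uncounted.

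The size cannot be put as an expected number of subjects, because the documents give no incidence of rhythm findings. The number of scheduled ECGs would not serve as a substitute, since it counts recordings rather than missed findings.

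A reader might also infer that any arrhythmia with a fast rate escapes Table 4. The calculation does not support that: under the assumed baseline, a tachycardia at 130 bpm escapes with a QT of 290 ms and is flagged through Bazett's correction at 320 ms. A different baseline would move that boundary. Bradyarrhythmias below 50 bpm are caught.

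The primary and secondary efficacy conclusions are not affected.

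**What to change.** In SAP 10.4, add two by-dose tabulations, each as number (%) of subjects:

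- subjects with a clinically abnormal ECG on double-blind treatment, stating whose reading defines it;
- subjects with a treatment-emergent rhythm finding, and other qualitative findings where these are collected, absent at the V2 second-morning baseline that 10.4 already uses for ECG change.

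If the sponsor prefers not to produce these, the omission should be declared and justified in SAP 12.1.

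Optionally, add a high or increasing heart-rate category to Table 4 so that fast rates are counted as well as summarised.

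The cost is a few lines of SAP text and one or two tables. Protocol 7.2.4.9 has the ECG data transferred electronically to the sponsor, and rhythm is among the items evaluated. Before the tables are specified, the ECG laboratory manual or data transfer specification should be checked for an overall interpretation and for coded qualitative terms.

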## 10.5 Other safety parameters of interest

### 10.5.1 Digit Symbol Substitution Test

The Digit Symbol Substitution Test® (DSST) is a measure of attention, perceptual speed, motor speed, visual scanning and memory. The total DSST score is the number of correct symbols entered.

Absolute change from baseline (mean of the two PSG morning assessments at V2, run-in period) to Days 1 and 2 (mean of the two PSG morning assessments for a given treatment period) in total DSST score will be summarized by gender and overall. Absolute values will also be summarized.

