1.3 Purpose and rationale of the study

1.3.1 Purpose of the study

The main purpose of this dose-response study is to define the ACT-541468 dose(s) that will show a favorable efficacy and safety profile and to assess the safety and tolerability of the compound in elderly subjects with insomnia disorder.

The dose to be studied in future clinical trials will be established based on the change in objectively assessed WASO and safety data, such as next-day residual effect from baseline versus placebo.

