10.3.5 Analysis of the safety variables

All safety analyses will be performed on the SS, by dose, using descriptive statistics. All safety data will be listed, with flags for quantitative abnormalities.

Observations and assessments (e.g., AEs, laboratory data) occurring within a treatment period (from the time of dosing to the time immediately prior to the next dose) will be assigned to the dose taken in that period.

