10.3.5.6 Other safety parameters of interest

Change from Baseline (mean of the two PSG nights at V2, run-in period) to Days 1 and 2 (mean of the two PSG treatment nights) in KSS, DSST[®], and SDS[®] will be summarized by dose.

The incidence of most severe suicidal ideation and suicidal behaviors according to the C-SSRS[®] will be summarized by dose.

All scales analyses will be performed according to their respective manual and interpretation guide.

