#### **4 GENERAL ANALYSIS CONSIDERATIONS**

Unless noted otherwise, all statistical summaries will be presented by dose group and in the following order: Placebo, ACT-541468 5 mg, ACT-541468 10 mg, ACT-541468 25 mg, ACT-541468 50 mg.

Categorical data will be summarized by frequency counts and percentages. Unless specified otherwise, percentages will be based on the total number of subjects in the corresponding dose group.

Continuous data will be summarized using descriptive statistics (N, mean, standard deviation, median, minimum and maximum).

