#### *First stage*

A linear mixed effects model (first stage model) will be used to calculate estimates for  $\hat{\mu}_d$  (i.e., least squares [LS] mean estimates for each ACT-541468 dose level and placebo) and  $\hat{S}$  (i.e., variance-covariance matrix of  $\hat{\mu}_d$ ).

The change from baseline in WASO (assumed to be normally distributed) will be modeled using a fixed effect for dose group (placebo and each ACT-541468 dose level), an additional fixed effect for period (five periods), a linear slope to adjust for WASO at baseline, and a random effect for subject.

The variance of the change from baseline in WASO is assumed to be constant across each dose group, therefore a compound symmetry structure for  $\hat{S}$  will be considered.

The LS mean for each treatment group will be displayed along with associated standard errors and 95% confidence intervals (CIs). For each ACT-541468 dose level comparison to placebo, the placebo-adjusted LS mean will be displayed along with associated standard error, 95% CI and unadjusted two-sided  $p$ -value.

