## 10 SAFETY ANALYSIS

Unless noted otherwise, the SS will be used for summaries and listings of safety data.

All safety data will be listed.

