### **10.5.2 Karolinska Sleepiness Scale**

The Karolinska Sleepiness Scale (KSS) is a 9-point scale. The scale has a range from 1 being ‘very alert’ to 9 being ‘very sleepy, great effort to keep awake, fighting sleep’.

Absolute change from baseline (mean of the two PSG morning assessments at V2, run-in period) to Days 1 and 2 (mean of the two PSG morning assessments for a given treatment period) in KSS will be summarized by gender and overall. Absolute values will also be summarized.

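### Next-day scales (DSST, KSS, SDS, VAS) get no dose-minus-placebo estimate with a confidence interval, although the SAP's own WASO model could supply one cheaply

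*SAP*

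**What the plan says.** - **Purpose.** Protocol 1.3.1 says the dose for later trials will rest on the change in objective WASO and on "safety data, such as next-day residual effect from baseline versus placebo". The next-day effect is an example, and no scale is named. Protocol 3.2 adds that each dose will be compared with placebo within every subject.
- **Protocol analysis.** Section 10.3.5: "All safety analyses will be performed on the SS, by dose, using descriptive statistics". Section 10.3.5.6: changes "in KSS, DSST[®], and SDS[®] will be summarized by dose".
- **SAP analysis of the scales.** SAP 10.5.1 says change "in total DSST score will be summarized by gender and overall"; SAP 10.5.2 says change "in KSS will be summarized by gender and overall"; SAP 10.5.3 does the same for SDS. SAP 9.9 covers the VAS items for morning sleepiness, daytime alertness and daytime function. Absolute values are also summarised in each case. SAP 4 sets the statistics: N, mean, SD, median, minimum and maximum.
- **Other next-day outputs.** SAP 10.7 plots DSST, KSS, SDS and the morning-sleepiness VAS against the 9–10 h concentration, without double-blind placebo and without an estimate. SAP 10.5.4 tabulates excessive sleepiness and time until safe to leave, by dose. SAP 10 states "All safety data will be listed".
- **WASO, by contrast.** For each dose against placebo, the first stage in SAP 7.3.2.2 says "the placebo-adjusted LS mean will be displayed along with associated standard error, 95% CI". The model has dose, period, baseline and a random subject effect.

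**The concern.** The dose decision weighs a sleep benefit against a next-day cost. The benefit side will carry a period-adjusted, placebo-corrected estimate with an interval at each dose. The cost side, on these six scales, will carry columns of means and SDs. The tables will not state how large an impairment relative to placebo each dose leaves possible in these elderly subjects.

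In a crossover, the precision of dose minus placebo depends on within-subject variation, which per-dose columns do not show directly. A reader must reconstruct it from several SDs or rework the listings. Listings-based differences are not adjusted for period. Learning is foreseen for DSST: Protocol 7.2.4.4 supplies eight versions to limit it, but six visits (V2 to V7) with two mornings each make 12 administrations, so versions must recur.

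**Working it through.** **1. The plan's own figure.** The only power figure concerns WASO (Protocol 10.5). Inputs: 50 subjects, 8% unavailable (so 46), maximum effect 25 min, SD 40, zero correlation, two-sided 5%, and the four candidate shapes. Simulation of the multiple contrast test gives 92.0%, 90.2%, 89.4% and 89.4%, mean 90.2%, against the stated 89–92% and 90%. It reproduces. No such figure is given for DSST, KSS, SDS or VAS.

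**2. Precision of the added estimate.** Half-width = t(0.975, about 176 df) × SD × √(2(1−ρ)/46), where SD is that of the change score. ρ, the correlation between changes at two doses, is an assumption.

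| ρ | 0 | 0.3 | 0.5 | 0.7 | 0.8 |
|---|---|---|---|---|---|
| Half-width (SD) | 0.41 | 0.34 | 0.29 | 0.23 | 0.18 |

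The difference detectable with 80% power is (1.96 + 0.84) × √(2(1−ρ)/46), that is 0.58 SD at ρ = 0 and 0.26 SD at ρ = 0.8.

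**3. What the planned tables allow.** Let each period value have within-subject variance s² and the baseline k·s², with a common subject effect. For DSST, KSS and SDS, each value is a two-morning mean.
- Change has variance (1+k)s², and two changes share covariance k·s², so ρ = k/(1+k).
- The paired SE is s√(2/n). With 45 completers (50 less the 10% dropout in Protocol 3.1), 1.96 × √(2/45) = 0.41, so the half-width is 0.41 s.
- The tables give Var(B), Var(Y) and Var(change) for baseline B and period value Y. Hence Cov(B,Y) = (Var B + Var Y − Var change)/2 and s² = Var Y − Cov(B,Y). No correlation need be guessed, provided the baseline SD is tabulated and baseline-to-period covariance equals period-to-period covariance.
- In simulation (n = 45, k from 0.5 to 2, between-subject variance 0.5 to 4 s²) this SE averages 0.97 to 1.00 of the true one. In the worst setting its 5–95% range is roughly 0.5 to 1.3, against 0.8 to 1.2 for an SE taken directly from paired differences.
- Cruder readings: SD of change/√n is √((1+k)/2) times the paired SE, that is 0.87, 1.00 and 1.22 for k = 0.5, 1 and 2. Treating columns as independent gives √(1+k), that is 1.22, 1.41 and 1.73.

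**4. What the listings allow.** Raw paired differences have the model's SE if there is no drift. With an assumed linear drift of t·s per period, the ratio is √(1 + v·t²/2), where v is the variance of (period of dose − period of placebo) over the five sequences of Protocol Table 1.

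| Dose | Period differences, sequences 1–5 | v | t = 0.25 | t = 0.5 |
|---|---|---|---|---|
| 5 mg | −1, 3, −2, 2, −2 | 4.4 | 1.07 | 1.24 |
| 10 mg | −3, −1, −1, 3, 2 | 4.8 | 1.07 | 1.26 |
| 25 mg | −2, 2, −3, 4, −1 | 6.8 | 1.10 | 1.36 |
| 50 mg | −4, 1, 1, 1, 1 | 4.0 | 1.06 | 1.22 |

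Each row averages 0, so drift adds spread but no bias with complete data. Random loss of 5 of 50 subjects during the study shifts the mean period of a dose against placebo by about 0.05 of a period, which is negligible.

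**The case against.** The case against is substantial, and much of it stands.

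- **Descriptive safety analysis is prespecified.** A reader might infer that the SAP contradicts the protocol or drops a promised analysis. The documents do not support that. Protocol 10.3.5 and 10.3.5.6 themselves plan descriptive summaries, and 1.3.1 offers next-day effect only as an example, with no numerical criterion. Protocol 7.2.4.8 uses the same phrase for the neurological examinations, whose related outcomes SAP 10.5.4 already tabulates.
- **The precision is not lost.** A reader might infer that it cannot be had without guessing a correlation. Step 3 shows otherwise: absolute-value SDs are tabulated too. What remains is an untested covariance assumption and a noisier SE.
- **The multipliers are hypothetical.** A reader might take 1.22 to 1.73, or 1.36 at 25 mg, as the loss. The first range arises only if someone treats crossover columns as independent, which no section proposes. Baseline and period are both two-morning means for DSST, KSS and SDS, so k = 1 is the natural value, and there SD/√n equals the paired SE. The drift rates are assumed; learning is mentioned for DSST alone among these scales.
- **The study is not powered for this.** Protocol 10.5 disclaims power for single doses against placebo. That is a reason to show the interval, but also a warning: an interval including 0 may be misread as no impairment.

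None of these points supplies the missing output. The SAP 10.7 plots exclude placebo, and neither the listings nor the tables give a period-adjusted contrast.

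**Conclusion.** The point holds as a worthwhile, inexpensive improvement. It is neither an error nor a contradiction, and no sample size, power figure or primary conclusion changes. For six next-day measures, the SAP plans no dose-minus-placebo estimate or interval, while its WASO model produces exactly that and every subject is due to receive placebo and all four doses.

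The size of what is lost cannot be stated, because the documents give no SD, correlation or drift for these scales. The added interval would have a half-width of about 0.18 to 0.41 SD of the change score at n = 46, for assumed ρ from 0.8 to 0. It would replace an approximation that needs a covariance assumption, or listings work that leaves any period effect in the spread. Column mean differences are already essentially unbiased. No dose decision has been shown to turn on the addition.

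**What to change.** Add one paragraph to SAP 10.5 and a matching sentence to SAP 9.9:

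- Fit the SAP 7.3.2.2 first-stage mixed model (dose, period, baseline, random subject) to change from baseline in DSST, KSS and SDS on the Safety Set, by dose received.
- Fit it also to the VAS next-day items, at minimum morning sleepiness, on the FAS, the set that SAP 9 uses.
- Report each dose minus double-blind placebo with a 95% CI, as estimation only, without p-values or multiplicity control.
- State beside the tables that the study was not powered for these comparisons and that an interval including 0 does not show absence of a next-day effect.
- Keep the descriptive tables. Leave the SAP 10.5.4 outcomes descriptive: they are yes/no or move in steps of about 30 minutes, which this model does not suit.

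The documents do not show whether the blind has been broken; SAP Final 2.0 already follows a dry-run review. If it has, label the analysis post hoc.

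Cost: a rerun of existing model code on data already collected, and about four to six extra tables. The downsides are a normal approximation for the 9-point KSS and the risk that intervals including 0 are misread.
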